10.8 ADDITIONAL EVALUATIONS

- 10.8.1 In the event that balance between the treated and control groups is not sufficiently close to allow direct comparison, a multivariable analysis will be done in which the MAE rates between the two groups will be compared with the treatment group, propensity score class, and the covariates for which balance was not satisfactorily achieved. This exploratory analysis will determine if treatment retains statistical significance in the presence of the propensity score class adjustment and covariate adjustment for those covariates unsatisfactorily balanced by the propensity score. Also, special interest will be directed to whether the covariates unsatisfactorily balanced have a statistically significant relationship to the MAE rate.
- 10.8.2 *Procedural and In-Hospital Evaluations:* The need for blood transfusion, estimated blood loss volume, contrast volume, fluoroscopy time, procedure time (and other intraprocedural times), anesthesia time and type, frequency of concomitant procedures, ICU time, and time to hospital discharge will be presented descriptively. Qualitative variables will be presented with rate. Quantitative variables will be presented with mean, standard deviation, median, minimum and maximum.
- 10.8.3 *Mortality:* The proportion of patients with mortality (all-cause and aneurysm-related) will be presented at 30 days and at each subsequent timepoint for which data are available (i.e., six months, and annually at years 1 through 5). A descriptive analysis and a Kaplan-Meier analysis of all-cause and aneurysm-related mortality through 30 days and for late follow-up including 30 days will be presented.
- 10.8.4 *Major Adverse Events (MAE) Individual Components:* The proportion of patients experiencing each category of MAE within 30 days and after 30 days at each subsequent timepoint for which data are available will be presented.
- 10.8.5 *Composite Late MAEs(after 30 days):* The proportion of patients experiencing an MAE after 30 days will be presented at each subsequent timepoint for which data are available. A descriptive analysis and a Kaplan-Meier analysis of the MAE composite will be presented for follow-up through 30 days and for late follow-up including 30 days. The descriptive analysis will present the rates for the composite MAE and each individual adverse event that is part of the composite.
- 10.8.6 *Aneurysm Rupture:* The proportion of patients experiencing a rupture of the aneurysm will be presented at 30 days and at each subsequent timepoint for which data are available.
- 10.8.7 *Conversion to Open Repair:* The proportion of patients undergoing surgical conversion to open repair will be presented at 30 days and at each subsequent timepoint for which data are available.
- 10.8.8 *Serious Adverse Events (SAEs):* The proportion of patients experiencing an SAE grouped in categories by body system type will be presented descriptively by timepoint. The SAEs to be studied in this way include blood and lymphatic disorders, bleeding, cardiac, gastrointestinal, genitourinary, hepatobiliary, infection,

multiorgan failure, musculoskeletal, neoplasm, neurological, renal, respiratory, secondary procedures, skin, vascular, other, and overall.

10.8.9 *Non-serious AEs:* The proportion of patients experiencing a non-serious AE grouped in categories by body system type will be presented descriptively by timepoint. The AEs to be studied in this way include blood and lymphatic disorders, bleeding, cardiac, gastrointestinal, genitourinary, hepatobiliary, infection, multiorgan failure, musculoskeletal, neoplasm, neurological, renal, respiratory, secondary procedures, skin, vascular, other, and overall.

10.8.10 *Distal Blood Flow Evaluations:* A descriptive analysis of distal blood flow and any changes at 30 days and at each subsequent timepoint for which data are available will be done based on ankle brachial index (ABI) evaluations. A determination will be made from the data as to whether the occurrence was associated with an SAE or device malfunction.

10.8.11 *Endograft Performance:* A descriptive analysis of the following will be done based on Core Lab evaluations at 30 days and at each subsequent timepoint for which data are available. A determination will be made from the data as to whether any observation was associated with an SAE or device malfunction.

Aneurysm Size Change: The changes in aneurysm size from the first post-operative evaluation will be presented descriptively at each subsequent follow-up. The maximum diameter parameter will be used for the analysis because it is the basis for comparison to other studies with endografts. For each follow-up interval, the number and percent of patients with increased sac diameter (>5 mm), stable sac diameter (\leq 5 mm), or decreased sac diameter (>5 mm) will be presented.

Incidence of Migration: The occurrence of migration (>10mm movement from the original implant location as determined on the first post-operative scan) will be presented descriptively at each follow-up.

Incidence of Endoleak: The occurrence of endoleak (any type or location, new and persistent) will be presented descriptively at each follow-up.

Incidence of Limb Occlusion: The occurrence of endoleak (any type or location, new and persistent) will be presented descriptively at each follow-up.

10.8.12 *Renal Function Evaluations:* A descriptive analysis of renal function will be done based on serum creatinine levels and calculated estimated glomerular filtration rate (eGFR) at 30 days and at each subsequent timepoint for which data are available. Renal dysfunction will be defined as a reduction in eGFR of >30% from the preoperative value.

10.8.13 *Renal Stent Graft Patency and Integrity:* A descriptive analysis of device patent luminal flow, absence of stent fracture, kinking, stenosis, or occlusion [$>60\%$ luminal obstruction]), absence of graft failure, and absence of renal artery infarct $>30\%$ will be determined by contrast-enhanced CT scan, as assessed by the independent core laboratory at 30 days and at each subsequent timepoint for which

data are available. A determination will be made from the data as to whether the occurrence was associated with an SAE or device malfunction.

- 10.8.14 *Stent Graft (fenestrated/bifurcated) Patency and Integrity:* A descriptive analysis of device patent luminal flow, absence of stent fracture, kinking, or occlusion, and absence of graft failure will be determined by contrast-enhanced CT scan, as assessed by the independent core laboratory at 30 days and at each subsequent timepoint for which data are available. A determination will be made from the data as to whether the occurrence was associated with an SAE or device malfunction.
- 10.8.15 *Secondary Procedures:* A descriptive analysis of secondary procedures for resolution of endoleak, limb occlusion, migration, aneurysm sac expansion, and/or a device defect will be done at 30 days and at each subsequent timepoint for which data are available.

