- Adverse Events: All serious and non-serious events within 30 days, at 6 months, and at 1 to 5 years;
- Distal blood flow as assessed by ankle-brachial index evaluations pre-discharge and at 30 days, 6 months, and years 1 to 5;
- Endograft performance (aneurysm sac diameter change from the first post-operative visit; device migration; incidence of endoleak; incidence of limb occlusion) at 30 days, 6 months, and years 1 to 5;
- Renal function as assessed by estimated glomerular filtration rate (eGFR) pre-discharge and at 30 days, 6 months, and years 1 to 5;
- Renal stent graft patency and integrity at 30 days, 6 months, and years 1 to 5
- Stent graft (fenestrated/bifurcated) patency and integrity at 30 days, 6 months, and years 1 to 5;
- Secondary procedures within 30 days, at six months, and at years 1 through 5 for resolution of endoleak, limb occlusion, migration, aneurysm sac expansion and/or a device defect.

Schedule of Tests: Pre-procedural high resolution, contrast-enhanced CT scan evaluation to determine anatomical eligibility for enrollment will be performed within three months of the procedure. A physical exam and laboratory testing will be performed prior to the procedure. Following ethics committee/IRB approval

[†]Defined as all-cause death, bowel ischemia; myocardial infarction, paraplegia, renal failure, and respiratory failure, stroke, and blood loss >1,000cc. Refer to protocol §8.7.7 for detailed definitions.

[‡]Refer to protocol §8.7.7 for detailed definitions.

and patient written informed consent, the patient will be screened for eligibility. Patients will be followed procedurally and to hospital discharge, and will then be followed at intervals: 1 month; 6 months; 1 year; and annually to 5 years. Tests and evaluations:

Schedule of Tests:	Screening/ Baseline	Procedure (Day 0)	Pre- Discharge	1 Month*	6 Months*	1 to 5 Years*
Physical Exam [†]	x		x	x	x	x
Blood Labs [‡]	x		x	x	x	x
Contrast-Enhanced CT Scan [¥]	x			x	x	x
Ankle Brachial Index	x		x	x	x	x
Adverse Events		x	x	x	x	x

[†]The physical exam includes overall health and physical assessment and vital signs.

[‡]Blood labs include serum creatinine, blood urea nitrogen, hematocrit, and hemoglobin.

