6.3. ADDITIONAL EVALUATIONS

Additional evaluations include:

- **Procedural and In-Hospital Evaluations:**
 - Volume of contrast media used;
 - Fluoroscopy time;
 - Total procedure time;[‡]
 - Time in ICU;[§]
 - Estimated blood loss;
 - % requiring blood transfusion;
 - Anesthesia time;[¥]
 - Time to hospital discharge;[£]
- **Mortality**, all-cause and aneurysm-related, within 30 days, at six months, and years 1 through 5;
- **MAE Individual Components** within 30 days, at six months, and years 1 through 5;
- **Composite MAEs** after 30 days ,at six months, and years 1 through 5;
- **Aneurysm Rupture** within 30 days, at six months, and years 1 through 5;
- **Conversion to Open Repair** within 30 days, at six months, and years 1 through 5;
- **Adverse Events** (serious and non-serious) within 30 days, at six months, and years 1 through 5;
- **Distal Blood Flow** pre-discharge and at 30 days, six months, and years 1 through 5 as determined by ankle-brachial index measurements and changes over time.
- **Endograft Performance** (aneurysm sac diameter change from the first post-operative visit; device migration; incidence of endoleak) at 30 days, 6 months, and years 1 to 5;
- **Renal Function** pre-discharge and at 30 days, six months, and years 1 through 5, as assessed by the estimated glomerular filtration rate (eGFR) and changes over time;
- **Renal Stent Graft Patency and Integrity** within 30 days, at six months, and years 1 through 5, as determined by contrast-enhanced CT scan, and as assessed by the independent core laboratory, inclusive of:
 - Patent luminal flow
 - Absence of kinking, stenosis, or occlusion (>60%)
 - Absence of stent fracture
 - Absence of graft failure
 - Absence of renal infarct >30%

[‡]Elapsed time from the first break of skin to final closure (i.e., skin to skin time).

[¥]Elapsed time from the initiation to the end of the anesthesia protocol.

[§]Elapsed time from the first administration of anesthesia to release from the ICU or post-anesthesia care unit providing ICU-level care. If the patient is not admitted to the ICU, this is defined as 0 hours.

[£]Elapsed time from initiation of the procedure to physical discharge from the hospital.

- **Stent Graft (Fenestrated/Bifurcated) Patency and Integrity** within 30 days, at six months, and at years 1 through 5, as determined by contrast-enhanced CT scan, and as assessed by the independent core laboratory, inclusive of:
 - Patent luminal flow
 - Absence of kinking or occlusion

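### Section 10.8.11 repeats the endoleak rule under the limb-occlusion heading, so no section reports limb-occlusion incidence as such

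*Combined protocol and SAP*

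**What the plan says.** The synopsis (section 3, Additional Evaluations) treats limb occlusion as an Endograft Performance item in its own right, next to endoleak, with a full visit schedule: "device migration; incidence of endoleak; incidence of limb occlusion) at 30 days, 6 months, and years 1 to 5".

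Section 6.3 gives the corresponding list in the protocol body, without limb occlusion: "aneurysm sac diameter change from the first post-operative visit; device migration; incidence of endoleak) at 30 days, 6 months, and years 1 to 5".

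Section 10.8.11 opens with the basis for all the Endograft Performance analyses: "A descriptive analysis of the following will be done based on Core Lab evaluations at 30 days and at each subsequent timepoint". Two of its entries stand one after the other. The first, on endoleak, reads "Incidence of Endoleak: The occurrence of endoleak (any type or location, new and persistent) will be presented descriptively at each follow-up". The second, which by its heading should deal with limb occlusion, reads "Incidence of Limb Occlusion: The occurrence of endoleak (any type or location, new and persistent) will be presented descriptively at each follow-up".

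Section 10.8.14 separately plans, for the fenestrated and bifurcated stent grafts, "A descriptive analysis of device patent luminal flow, absence of stent fracture, kinking, or occlusion, and absence of graft failure", read by the core laboratory on contrast CT at 30 days and later timepoints. Section 10.8.15 describes secondary procedures, with limb occlusion among the reasons for them. Section 8.7.7 defines Stent Graft Occlusion for the aortic or renal graft, identified either by an intervention for it or by Core Laboratory report. It has no separate entry for limb occlusion.

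**The concern.** The entry's heading names one event and its rule tabulates another. A programmer working strictly from 10.8.11 would produce a limb-occlusion table filled with endoleak counts. A reader of the report could take those counts for occlusions. If the slip were noticed only at analysis, someone would have to choose a definition of limb occlusion after the data were in hand.

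The rest of the document does not fully settle what was meant. The synopsis includes the item, 6.3 leaves it out of the matching list, and 10.8.11 has the heading with the wrong content. Limb occlusion is also one of the five reasons for secondary intervention that count against Treatment Success, but it enters that endpoint only when it is treated. A plain incidence that includes untreated cases is the natural companion to that component.

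**Working it through.** No alpha, rate, margin or sample size is involved, so the check compares texts.

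**Step 1: the two entries in 10.8.11.** Remove the headings and compare the endoleak and limb-occlusion sentences. They are identical: same event, same parenthesis on type and persistence, same presentation. The parenthesis fits endoleak and has no evident meaning for a limb occlusion. This points to a copying slip rather than a deliberate choice.

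**Step 2: what was intended.** The synopsis schedule covers 30 days, 6 months and five annual visits, or 1 + 1 + 5 = 7 timepoints, with limb occlusion listed separately from endoleak. The surviving heading in 10.8.11 agrees with the synopsis. The Endograft Performance list in 6.3 does not.

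**Step 3: whether another section supplies the incidence.**

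| Place | What it would show | Limb-occlusion incidence as such? |
|---|---|---|
| 10.8.14, stent graft patency and integrity | Occlusion of the fenestrated/bifurcated device on core-lab CT, treated or not | No; device level, with no breakdown by limb |
| 10.8.15, secondary procedures | Interventions done for limb occlusion | No; treated cases only |
| 6.2 and 10.7, Treatment Success | Failure through such an intervention | No; treated cases only, inside a composite |
| 10.8.8 and 10.8.9, adverse events | Events grouped by body system, including a vascular group | No |
| 10.8.10, distal blood flow | Ankle-brachial index and its changes | No; indirect |
| 8.7.7, Stent Graft Occlusion | A definition for aortic or renal grafts | No; a definition, not a tabulation |

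**Step 4: whether a limb occlusion falls within 10.8.14.** Section 7.1 gives limb lengths and diameters as dimensions of the bifurcated device and refers to the body and limbs of the stent graft. An occluded limb seen on follow-up CT is therefore an occlusion of the bifurcated device. It belongs in 10.8.14 whether or not it was treated.

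**Result.** Endoleak is specified under two headings and limb-occlusion incidence under none. The underlying events still have a route into the report, but without a line of their own.

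**The case against.** The strongest reply is that this is an editorial slip with a small effect. The heading and the synopsis make the intent plain, the evaluation is purely descriptive, and limb occlusions do not vanish from the analysis. Section 10.8.14 covers occlusion of the bifurcated device from core-lab CT over the same follow-up schedule and does not depend on intervention. The 8.7.7 definition includes occlusions reported by the Core Laboratory, so untreated cases fall within a defined event. Treated cases appear in 10.8.15. Graft or lower-limb arterial occlusion is also an anticipated adverse event in 8.7.4, with a vascular category in the event tables. Section 6.3 itself keeps occlusion under stent graft patency and limb occlusion under secondary procedures; only its Endograft Performance bullet omits it.

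Most of this stands, and it rules out stronger conclusions that a reader might draw. One is that limb occlusion is never analysed, or is lost at all seven scheduled timepoints. Another is that 10.8.11 is the only place where an untreated occlusion could be seen. The documents support neither, because 10.8.14 can capture these occlusions at device level.

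The reply does not remove the error. Section 10.8.14 promises no limb breakdown, so a limb occlusion there could not be told apart from occlusion elsewhere in the device. An obvious intent also does not make the written rule executable, and with no limb-specific definition the analyst would still have to supply one.

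**Conclusion.** The point holds in a limited form. The rule under the limb-occlusion heading is wrong as written: it duplicates the endoleak tabulation, and the separate limb-specific incidence promised in the synopsis has no analysis. Section 6.3 disagrees with the synopsis on whether the item belongs to Endograft Performance.

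The size is one descriptive line in an additional evaluation. A reader might infer that the primary effectiveness result is affected because limb occlusion is named in Treatment Success. It is not: that endpoint counts interventions, and its definition, 80% performance goal and sample size do not depend on 10.8.11. The safety comparison is likewise unaffected.

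The conclusion rests on two readings: that the synopsis and the 10.8.11 heading express the intended content, and that limbs count as part of the bifurcated device under 10.8.14, as the description in 7.1 indicates.

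**What to change.** 1. In 10.8.11, replace the sentence under the limb-occlusion heading with wording such as: *Limb occlusion, meaning Stent Graft Occlusion as defined in 8.7.7 that involves a limb of the bifurcated stent graft or a limb extension, will be tabulated descriptively at each follow-up.*
2. State that cases identified by intervention under that definition count in addition to Core Lab reports. Without this, the entry would conflict with the opening of 10.8.11, which bases the section on Core Lab evaluations. Treated cases will then also appear in 10.8.15, which is acceptable because that section counts procedures and this one counts occurrences.
3. Add limb occlusion to the Endograft Performance list in 6.3 so that it matches the synopsis.

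The cost is a few lines of protocol and SAP wording. No new data collection appears to be needed: contrast CT is already scheduled at every follow-up visit, and 8.7.3 already asks sites to record the vessel segment and procedure for secondary interventions. No sample size, test or error rate changes.

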4.3. TRIAL DESIGN

This is a multicenter, prospective, single arm clinical trial. Patients with JAA/PAA who are suitable candidates for endovascular repair using the Endologix Fenestrated Stent Graft System will be considered for enrollment.

After this protocol and the patient informed consent form are reviewed and approved by the local Ethics Committee or responsible Institutional Review Board, potential patients will be offered participation in the study. This will be accomplished through the patient's reading of the informed consent form in the patient's native language and discussion of the study with the patient by the investigator and site personnel. Agreement to participate and to attend all follow-up visits will be documented with the patient's signature on the informed consent form, with appropriate signatures of the site investigator and an impartial witness.

After providing written informed consent, screening and eligibility determinations will be performed. Patients will undergo a high resolution, contrast-enhanced computed tomography angiography (CT) scan of the relevant aortic and aortoiliac vasculature within three months of the scheduled procedure. Evaluation of the aortic and vascular anatomy suitability per this protocol, as depicted on the CT scan, will be performed by the site investigator and by an independent core laboratory. Other tests include a physical examination, review of patient medical history for exclusionary conditions, selected blood chemistry and hematology analyses, and ankle-brachial index determination.

Upon acceptance for enrollment, patients will be scheduled for the endovascular repair procedure.

Note: An investigational site may not enroll more than 20% of the total Trial Phase enrollment.

Following patient discharge from the hospital, the first follow-up visit will be made at one month (± 2 weeks). A CT scan will be performed to assess aneurysm morphology and device integrity and patency, as well as the status of the renal arteries and implanted stent grafts. Subsequent follow-up will be made at six months, one year, and annually to five years.

Continued patient follow-up beyond five years is outside of the scope of this study. Nonetheless, all patients should be monitored and evaluated per the institutional standards of care for patients who receive an endovascular stent graft.

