8.4. SCHEDULE OF MEASUREMENTS

A summary of the tests and measurements to be conducted pre-study/at baseline, operatively, prior to discharge, and during follow-up is illustrated in the following chart.

Schedule of Tests:	Screening/ Baseline	Procedure (Day 0)	Pre- Discharge	1 Month*	6 Months*	1 to 5 Years*
Physical Exam [†]	x		x	x	x	x
Blood Labs [‡]	x		x	x	x	x
Contrast-Enhanced CT Scan [¥]	x			x	x	x
Ankle Brachial Index	x		x	x	x	x
Adverse Events		x	x	x	x	x

[†]The physical exam includes overall health and physical assessment and vital signs.

[figure not shown]
[‡]Blood labs include serum creatinine, blood urea nitrogen, hematocrit, and hemoglobin.

[¥]The baseline high resolution, contrast-enhanced CT scan (2mm or less slice spacing) performed within three months prior to enrollment will be reviewed by the independent core lab for patient eligibility determination. Evaluations of endograft performance, renal stent graft patency and integrity, and stent graft patency and integrity will be made based upon post-operative CT scan evaluations by the core laboratory.

*Follow-up windows are ±2 weeks (1 month visit); ±1 month (6 month visit); ±2 months (Year 1 visit); ±3 months (Years 2 through 5 visits)

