8.7.7. Clinical Events Committee Review

Overview

The clinical events committee (CEC) identified in §2 consists of at least three physicians who will serve as independent experts responsible for evaluation and categorization of adverse events reported by the investigators in the trial. Analyses of events described in this protocol will be based on the CEC-determined categorization.

The primary purpose of these individuals is to ensure a consistent, independent review of events and their clinical significance using standardized criteria and definitions. A curriculum vita for each CEC member is maintained by Endologix, and is available for regulatory review. Due to the need for independence, these individuals may not participate in this trial as investigators, and may not hold significant material, financial or other interests which create a potential conflict with respect to this role, including but not limited to significant equity

interest in Endologix.

Process

Endologix will provide independently to the CEC the complete case report form event text that details all deaths and the events as reported by the clinical site investigators. This information will be provided without identification of the site name, and will identify patients by identification number and initials only. Non-serious events or events that are reported as clearly unrelated events will not be assessed by the CEC. The CEC will review events and any follow-up data requested from Endologix. This may include copies of such documents as progress notes, operative notes, discharge summaries, death summaries, and autopsy reports.

The CEC will document the event categorization for each event individually. Meeting notes and supporting information, requests for documentation, etc. will be maintained.

Event Definitions

The following event definitions will be applied to the Primary Endpoint Analysis during this study. Where possible, events will be categorized as being related to the endovascular procedure/bifurcated device, to the fenestrated device, or to the renal stent graft device.

- *Death*: Any death occurring during the study period, regardless of cause.

Death will be further subcategorized as early (within 30 calendar days from the date of the procedure) or late (>30 days). It will also be subcategorized as aneurysm-related or not aneurysm-related.

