 - *Conversion to Open Repair*: open surgical repair of the abdominal aortic aneurysm due to unsuccessful delivery or deployment of the stent graft, due to complications or other clinical situations that precluded successful endovascular treatment, or at any time following initial successful endovascular treatment for any reason.
 - *Cardiac Morbidity*: acute myocardial infarction (diagnosed based on measured levels of one or more cardiac biomarkers in comparison to laboratory reference ranges); new onset heart failure (an acute episode or exacerbation of existing low cardiac output accompanied by distal and/or pulmonary edema); intractable or malignant arrhythmia requiring cardioversion or pacemaker placement; or coronary intervention (coronary artery bypass grafting [CABG] or percutaneous coronary intervention [PCI]).
 - *Clinically Significant Device Migration*: Core Lab reported aortic stent graft movement >10mm from the original implant location resulting in an intervention or in a serious complication.
 - *Renal Dysfunction*: a reduction in the estimated glomerular filtration rate (eGFR) of >30% from the preoperative value;
 - *Secondary Procedure*: any non-diagnostic intervention after the index procedure intended to correct or repair an endoleak, limb occlusion, migration, aneurysm sac expansion and/or a device defect;
 - *Stent Graft Occlusion*: Intervention for aortic or renal stent graft occlusion or as reported by the Core Laboratory.

- *Transient Ischemic Attack*: a sudden development of neurological deficit due to vascular lesions of *the* brain such as hemorrhage, embolism, or thrombosis that persists for <24 hours.
- *Type I/III/IV Endoleak*: Core Lab reported endoleak: between the endograft and the vessel either at the proximal attachment point (Type IA) or at the distal attachment point (Type IB); between endograft components (Type III); or transgraft (Type IV)
- *Type II Endoleak*: Core Lab reported endoleak emanating from a patent collateral vessel (e.g., inferior mesenteric artery; lumbar artery; etc.).

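### Patency in 6.3 and 10.8.13–14 is read from Core Lab CT alone, so a renal stent graft that occluded and was reopened before the next scan is tabulated as patent, although 8.7.7 counts it as an occlusion

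*Combined protocol and SAP*

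**What the plan says.** **The event.** Section 8.7.7 defines Stent Graft Occlusion as "Intervention for aortic or renal stent graft occlusion or as reported by the Core Laboratory". Either route is enough. The list of definitions opens with a statement of scope: "The following event definitions will be applied to the Primary Endpoint Analysis during this study".

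**The patency evaluations.** Section 6.3 sets out renal stent graft patency and, separately, aortic (fenestrated/bifurcated) graft patency, each "as determined by contrast-enhanced CT scan, and as assessed by the independent core laboratory, inclusive of" patent flow and absence of occlusion. The footnote to the 8.4 schedule says that evaluations of "stent graft patency and integrity will be made based upon post-operative CT scan evaluations by the core laboratory"; the synopsis carries the same footnote. Sections 10.8.13 (renal) and 10.8.14 (aortic) say that the components "will be determined by contrast-enhanced CT scan, as assessed by the independent core laboratory at 30 days" and at each later timepoint. Both end with "A determination will be made from the data as to whether the occurrence was associated with an SAE or device malfunction".

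**The scans.** Section 4.3 places the first CT at one month and then states: "Subsequent follow-up will be made at six months, one year, and annually to five years".

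**Reinterventions elsewhere.** Treatment Success (6.2), the Secondary Procedure definition (8.7.7) and the secondary-procedure analysis (10.8.15) share one list of reasons: endoleak, limb occlusion, migration, sac expansion and device defect. Renal stent graft occlusion is not on it.

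**The concern.** Section 7.1 gives the purpose of the renal stent graft as keeping the renal arteries open, and 7.3 lists it as an investigational device. Section 10.8.13 is the evaluation that measures this directly. As written, it places grafts that never occluded and grafts that occluded and were reopened on one line, without saying so. Someone who reads the patency table as the share of renal grafts that stayed open would take too favourable a view of the device. The number of occlusions by the protocol's own definition would not be reported under that definition anywhere.

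**Working it through.** The plan gives no occlusion or patency rate, so there is no figure to reproduce. The check sets the sections side by side.

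**1. One course of events under each rule.** Suppose a renal graft is open on the 1-year CT, occludes, is reopened by an intervention, and is open on the 2-year CT.

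| Place | How the graft is scored |
|---|---|
| 8.7.7 Stent Graft Occlusion | occlusion (intervention route) |
| 6.3, 8.4 footnote, 10.8.13 at year 2 | patent |
| 6.2 Treatment Success, 10.8.15 | not named; enters only if classed as a device defect |
| 10.8.8–10.8.9 SAE and AE tables | counted under a broad category such as renal, vascular or secondary procedures |

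Likewise, a graft occluded on one visit's CT and reopened afterwards returns to patent at the next visit. Nothing carries the earlier occlusion forward.

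**2. Does any other sentence close the gap?**
- The closing sentence of 10.8.13 and 10.8.14 asks whether an occurrence was linked to an SAE or malfunction. It classifies a finding and does not add one that the CT did not show.
- No Section 10 analysis uses the 8.7.7 occlusion definition by name.
- The limb-occlusion entry in 10.8.11 repeats the endoleak text, so it does not help.
- For the aortic graft, a reintervention for limb occlusion fails Treatment Success in 6.2 and is counted in 10.8.15. That part is largely covered. The renal part is not.

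**3. How long can pass between scans.** By the visit days in 8.6.7, nominal gaps are 180 − 30 = 150 days, 365 − 180 = 185 days, then 365 days. Within the allowed windows, a gap between two annual visits after year 2 can reach 365 + 90 + 90 = 545 days.

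**4. Direction and size.** For the same set of patients, let o be the share with a graft occluded on the visit CT, and q the share with all grafts open on that CT but an earlier occlusion that was reopened.

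- CT patency = 1 − o
- Patency with 8.7.7 occlusions counted = 1 − o − q
- Difference = q, which cannot be negative

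The direction needs no assumption. The size is q itself, which the documents do not give. For assumed values, with the 82 evaluable and 97 enrolled patients of 10.7.2:

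| Assumed q | Points overstated | q × 82 | q × 97 |
|---|---|---|---|
| 1% | 1 | 0.8 | 1.0 |
| 2% | 2 | 1.6 | 1.9 |
| 5% | 5 | 4.1 | 4.9 |
| 10% | 10 | 8.2 | 9.7 |

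For example, with o = 5% and q = 5%, CT patency is 95% and the figure counting interventions is 90%.

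**The case against.** The strongest reply is that these are two different measures. One is an adjudicated event, and its definition is tied to the primary endpoint analysis. The other is an imaging status at a timepoint, and 6.3, 8.4, 10.8 and the synopsis state it consistently. Nothing in the documents says that patency means never occluded. This stands: a reader might infer that the sections contradict each other or that CT patency is the wrong measure, and the text supports neither. It does not remove the gap. Stent graft occlusion is not itself a component of either primary endpoint, so if the scope sentence is taken strictly, the renal part of the definition is used nowhere.

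A reader might also infer that reopened occlusions vanish from the trial. They do not. Stent graft and renal artery occlusion are listed anticipated events (8.7.4), secondary treatments are to be recorded with vessel segment and procedure (8.7.3), and SAEs are tabulated by timepoint (10.8.8). But body-system tables yield no patency or occlusion rate.

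Nor is it certain that only scheduled scans are read. Sections 8.6.7 and 11.1(d) send submitted CT scans to the Core Lab, so a scan that diagnosed an occlusion could be read there. The plan does not say how an off-visit finding would enter a by-visit table. A renal infarct above 30% would still fail the 10.8.13 composite after reopening, but that captures only some cases.

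Finally, a reader might infer that sites which re-treat more would look better. No by-site patency analysis is planned, so this has no basis in the documents.

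**Conclusion.** The point holds, mainly for the renal stent graft. The CT-based patency tables count a graft reopened before the scan as patent, the plan does not label them so, and no analysis reports occlusion as 8.7.7 defines it. For the aortic graft the gap is smaller, because limb-occlusion reinterventions are counted elsewhere.

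The evaluation is descriptive, with no comparator or performance goal. It would be wrong to infer any effect on a primary test, alpha, power or the sample size of 97. The favourable direction follows from the definitions alone. The size does not: every value of q above is an assumption, and expressing the bias in standard errors would only restate assumed rates.

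The change is worth making because it affects the reported performance of an investigational component and needs no new data collection.

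**What to change.** 1. Keep the CT-based figure in 10.8.13 and 10.8.14, labelled as patency at the scan, including re-treated grafts.
2. Add to 10.8.13, and to 10.8.14 for the aortic graft, freedom from occlusion by the 8.7.7 definition. The event is the first Core Lab-reported occlusion or the first intervention for occlusion, whichever comes first, and later reopening does not reset it. Report it per graft and per patient by Kaplan-Meier, censored at death or last follow-up. Date an event by the intervention or by the scan that showed it.
3. State the threshold for a Core Lab-reported renal occlusion. Sections 6.3 and 10.8.13 use more than 60% obstruction; 8.7.7 gives none.
4. Align the synopsis, 6.3 and the 8.4 footnote, so that they no longer present CT as the only source.

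The cost is wording in these places and one more tabulation. Interventions are already recorded on the adverse event form, so no visit or scan is added. The reported rate becomes somewhat less favourable.
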